14.4 Follow-up

Follow up to determine breastfeeding status will be undertaken at 8-10 weeks after birth.

15 Statistical considerations

15.1 Randomisation

Not applicable.

15.2 Sample size

This feasibility study is not powered to detect statistical significance.

16 Analysis

Objective 1

Descriptive statistics will be used to show the current range of UK BFPS using data generated from the web-based survey of service providers. A narrative synthesis will be used to critique and summarise the characteristics of UK BFPS and any underpinning theoretical models.

Objective 2

Focus groups and interviews will be audio recorded and transcribed verbatim. Transcripts will be input into NVivo 10, and will be analysed using framework analysis (87) based on concepts within the Behaviour Change Wheel framework (9). This will allow the data to be analysed in a

structured way which is particularly helpful during intervention development and evaluation. The coding framework will include the items on the topic guide, as well as additional codes including barriers and facilitators to implementing and using the intervention. A random sample of 30% of transcripts will be coded by a second researcher, and any inconsistencies will be discussed and resolved.

Objective 3

We will map the theoretical models identified in the evidence review (objective 1) and the results from the qualitative work (objective 2) against the Behaviour Change Wheel framework (9) to specify the relevant sources of behaviour and corresponding intervention functions, and develop a logic model for the intervention.

Objective 4 – Quantitative data

We will use the quantitative data generated from objective 4 of the study to describe intervention uptake by mothers, completion of scheduled contacts with peer-supporters according to age-group and parity, recruitment and retention of peer-supporters, completeness of peer supporter diaries, follow-up of participants at 8 weeks, breastfeeding rates at initiation and at 8 weeks and other outcome measures described in Table 1, using percentages and 95% confidence intervals for categorical data and mean, standard deviation (s.d.) and 95% confidence intervals for continuous data. Thus summary data for the whole group and by site will provide information relevant to inform a full trial. The inter-class correlation will be estimated from the site data regarding variation in breast feeding outcome using ANOVA. We will describe completeness of data collected according to the different data collection methods described in appendix 1.

Objective 4 – Qualitative data

Audio recordings of interviews from the process evaluation will be transcribed verbatim and analysed using framework analysis to assess feasibility and acceptability of applying MI in BFPS, look at possible mechanisms and contextual factors, and research processes. The analysis procedure will, consist of framework development, coding, displaying coded data together facilitated by NVivo 10, and drawing conclusions (54). Peer-supporter structured diaries will be analysed to examine differences in completion and delivery style at the peer supporter level, and to also inform the development of an economic evaluation framework alongside a possible full trial.

Objective 4 – Intervention fidelity

Fidelity assessment using audio recordings will be analysed for content domain coverage and MI competencies using thematic content coding and a validated scale that measures adherence to Motivational Interviewing techniques (Motivational Interviewing Treatment Integrity (MITI 3.1) (14, 15) . Within the MITI, a random 20-minute extract of the interaction is analysed for individual behaviours, and also a 'global' score to assess the quality of the interaction. This strategy is particularly suited to briefly assessing practitioner fidelity and has good inter-rater reliability (14). We will use researchers trained in the use of the MITI code to analyse audio recordings. In addition to the MITI, 15 full intervention recordings will be analysed for content domain coverage. The codes will be developed following the development phase of this study but we anticipate that it may include categories such as social and emotional support, breastfeeding information and other parenting information. 30% of both analyses will be coded by two researchers to ensure reliability.

Objective 5

We will undertake a preliminary assessment of costs of implementing the intervention by attaching costs to resources utilised from published sources with assessments of time and other intervention costs from peer supporters' structured diaries. Costs will be tabulated against the range of outcomes to be assessed. We will use these data collectively to inform the design and plan a full RCT to test the effectiveness on MI-based BFPS.

16.1 Data storage & retention

All data will be kept for 15 years in line with Cardiff University's Research Governance Framework Regulations for clinical research. These data will be stored confidentially on password protected servers maintained on the Cardiff University Network.

17 Study closure

The end of the study will be considered as the date on which the last participant has completed their follow-up assessment or the last qualitative interview, whichever is later.

18 Regulatory issues

18.1 Ethical and research governance approval

The study will be conducted in accordance with the recommendations for physicians involved in research on human participants adopted by the 18th World Medical Assembly, Helsinki 1964 and later revisions.

Multi-centre ethical approval for this trial/study was given by <<Name of REC TBC>>. Site specific assessments were conducted by NHS Trusts and Health Boards in line with current permissions systems in the UK.

Research governance approval will be granted by all participating NHS Trusts prior to the study start date.

18.2 Consent

Consent will be sought for participation in all aspects of the study which involve participants; development work (objective 2), feasibility testing (objective 4) and process evaluation (objective 4). Consent will only be considered informed following provision of adequate participant information and the potential participant having been given a chance to ask questions and discuss with friend and / or family, as desired. . Withdrawal from the study will have no detrimental impact on current and future treatment.

18.3 Confidentiality

The Chief Investigator and the research team will preserve the confidentiality of participants in accordance with the Data Protection Act 1998.

18.4 Indemnity

Cardiff University will provide indemnity and compensation in the event of a claim by, or on behalf of participants, for negligent harm as a result of the study design and/or in respect of the protocol authors/research team. Cardiff University does not provide compensation for non-negligent harm.

Participants in qualitative development work will be recruited from a mixture of community groups and NHS sites, and will be covered by Cardiff University's public liability cover. All participants in the feasibility study will be recruited at NHS sites and therefore the NHS indemnity scheme/NHS professional indemnity will apply with respect to claims arising from harm to participants at site management organisations.

18.5 Study sponsorship

Cardiff University will act as sponsor for trial. Delegated responsibilities will be assigned to the NHS trusts taking part in this study.

18.6 Funding

The National Institute for Health Research Health Technology Assessment (NIHR HTA) are funding this project (Ref 13/18/05).

Participants in the feasibility study who go on to take part in a qualitative interview as part of the process evaluation (n=30) will receive a £20 shopping voucher. No other incentives will be given.

18.7 Audits & inspections

The study is participant to inspection by the NIHR as the funding organisation. The study may also be participant to inspection and audit by Cardiff University under their remit as sponsor.

19 Study management

[name] will meet with the research team (study manager, [name], [name]) weekly to oversee the day-to-day study management. The study management group (all study co-applicants and collaborators) will meet monthly.

20 Data monitoring & quality assurance

The research management team ([name], [name], [name], [name], [name]) will be responsible for the strategy to ensure adherence to data take collection and the researcher will responsibility for its implementation. The research management team will monitor the quality of data collection through regular surveillance tailored to the data collection schedule, for quality (including response rates, frequency of data returns, completeness and accuracy) and develop specific follow-up tasks to address any issues.

Fidelity to intervention delivery will be assessed by audio recording of interactions between peer supporters and participants, and will be subjected to assessment to MI principles and content domain analysis.

20.1 SSC (Study Steering Committee)

The study will be overseen by an expert study steering group, chaired by [name] (Chair in Primary Care). Other members include a senior statistician ([name], a senior maternity care academic, [name] and [name]. The committee will meet during months 3,8,12 and 22. Members will be required to sign up to the remit and conditions as set out in the SSC Charter.

20.2 DMC (Data Monitoring Committee)

It is not necessary to appoint a DMC for this study. The study steering committee will undertake these functions.

21 Publication policy

In addition to the required final report and monograph for the HTA Programme, we will publish the main study results in international peerreviewed journals and present at national and international scientific meetings. With the assistance of our collaborators and service users we will disseminate the study findings to a wide NHS and general audience. This will include presentations at meetings and written executive summaries for key stakeholder groups such as maternity units, health visitor groups, general practices and service users.

All publications and presentations relating to the trial will be authorised by the research management team.

22 Milestones

Month \rightarrow	Befo	ore stud	ły																								
Research element	start	S		1	2	3	4	5	6	7	8	9	10	11	12	13	14	15	16	17	18	19	20	21	22	23	24
Ethics and R&D																											
Recruit steering group																											
Rapid evidence review																											
Stakeholder task and finish group meeting 1																											
Focus groups (parents)																											
Interviews (health professionals)																											
Focus group with peer-supporters																											
Data analysis (objective 2)																											
Mapping of evidence review (stakeholder task and finish group meetings 2-4)																											
Development of study materials																											
Recruitment of peer-supporters																											
Training peer-supporters																											
Peer-support ongoing supervision																											
Set-up recruitment in sites																											
Recruitment and intervention delivery																											
Qualitative interviews with mothers																											
Structured telephone interviews																											
Interviews with peer-supporters																											
Interviews with Health professionals																											
Data analysis (objective 4)																											
Health economic analysis (objective 5)																											
Writing up and recommendations for future trial																											
Trial Management Group meetings																											
Steering Group Meetings																											

23 Appendices

Appendix 1: Detailed search strategy

OVID MEDLINE search strategy

1. exp Breast Feeding/

2. (infant feed* or breast feed* or breastfeed* or breast-feed* or breast fed or infant fed).mp.

3. Milk, Human/

4. or/1-3

5. Peer Group/

6. (lay adj5 (expert* or worker* or person* or advisor* or consultant* or leader* or educator* or tutor* or instructor* or facilitator*)).tw.

7. (volunteer* adj5 (trained or aide*)).tw.

8. (peer adj5 (expert* or worker* or advisor* or consultant* or leader* or educator* or tutor* or instructor* or facilitator*)).tw.

9. (peer support* or peer group or peer*).mp.

10. volunteer counsellors.mp.

11. ((support* or befriend* or advice* or advis* or counsel* or help* or assist* or encourag* or meeting* or visit*

or program*) adj3 (peer support or lay worker* or voluntary worker*)).tw.

12. or/5-11

13. 4 and 12

14. 13 not (Algeria\$ or Egypt\$ or Liby\$ or Morocc\$ or Tunisia\$ or Western Sahara\$ or Angola\$ or Benin or Botswana\$ or Burkina Faso or Burundi or Cameroon or Cape Verde or Central African Republic or Chad or Comoros or Congo or Djibouti or Eritrea or Ethiopia\$ or Gabon or Gambia\$ or Ghana or Guinea or Keny\$ or Lesotho or Liberia or Madagasca\$ or Malawi or Mali or Mauritania or Mauritius or Mayotte or Mozambiq\$ or Namibia\$ or Niger or Nigeria\$ or Reunion or Rwand\$ or Saint Helena or Senegal or Seychelles or Sierra Leone or Somalia or South Africa\$ or Sudan or Swaziland or Tanzania or Togo or Ugand\$ or Zambia\$ or Zimbabw\$ or China or Chinese or Hong Kong or Macao or Mongolia\$ or

or Afghanistan or Armenia\$ or Azerbaijan or Bahrain or Cyprus or Cypriot or Georgia\$ or Iran\$ or Iraq\$ or Jordan\$ or Kazakhstan or Kuwait or Kyrgyzstan or Leban\$ or Oman or Pakistan\$ or Palestin\$ or Qatar or Saudi Arabia or Syria\$ or Tajikistan or Turkmenistan or United Arab Emirates or Uzbekistan or Yemen or Bangladesh\$ or Bhutan or British Indian Ocean Territory or Brunei Darussalam or Cambodia\$ or India\$ or Indonesia\$ or Lao

or People's Democratic Republic or Malaysia\$ or Maldives or Myanmar or Nepal or Philippin\$ or Singapore or Sri Lanka or Thai\$ or Timor Leste or Vietnam or Albania\$ or Andorra or Bosnia\$ or Herzegovina\$ or Bulgaria\$ or Croatia\$ or Faroe Islands or Greenland or Liechtenstein or Lithuani\$ or Macedonia or Malta or maltese or Romania or Serbia\$ or Montenegro or Svalbard or Argentina\$ or Belize or Bolivia\$ or Brazil\$ or Colombia\$ or Costa Rica\$ or Cuba or Ecuador or El Salvador or French Guiana or Guatemala\$ or Guyana or Haiti or Honduras or Jamaica\$ or Nicaragua\$ or Panama or Paraguay or Peru or Puerto Rico or Suriname or Uruguay or Venezuela or developing countr\$ or south America\$).ti,sh.

15. limit 14 to (humans and yr="2000 -Current")

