4. Assess the feasibility of providing MI based BFPS to women living in areas with high levels of social deprivation.

5. Assess the feasibility of collecting resource usage and costs associated with the implementation of the MI based BFPS intervention.

6. Make recommendations about the need and design of a full randomised controlled trial to test the effectiveness of MI based BFPS for breastfeeding maintenance compared with usual care.

6 Study design

The study period is two years from 1st September 2014.

1. Description of the range of BFPS interventions used in the UK

Objective: To identify, categorise and describe the range of BFPS interventions used in the UK (Objective1)

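### Line 14 of the MEDLINE search can drop UK-set studies that name Pakistani, Bangladeshi, Indian, Nigerian or Chinese mothers in the title, from a review meant to describe UK peer support

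*Protocol*

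**What the plan says.** Section 6, item 1 of the Protocol gives the aim of Objective 1: "To identify, categorise and describe the range of BFPS interventions used in the UK". Item 1.2 (Literature review) adds a search of fourteen databases and relevant websites for theory, barriers and facilitators, and economic evaluations. It states no exclusion by mothers' ethnicity or by country of study, and refers to Appendix 1 for the strategy.

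Appendix 1 shows one strategy, for OVID MEDLINE. Lines 1 to 13 build the set of records on both breastfeeding and peer or lay support. Line 14 subtracts from it: it opens "13 not (Algeria\$ or Egypt\$ or Liby\$ or Morocc" and closes "developing countr\$ or south America\$).ti,sh", so the listed terms are looked for in title and subject heading. Among them are "China or Chinese or Hong Kong or Macao", "Leban\$ or Oman or Pakistan\$ or Palestin" and "India\$ or Indonesia\$ or Lao". Line 15 limits set 14 to human studies from 2000 onwards.

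**The concern.** The list appears designed to remove studies by setting, but it matches words, and several of those words describe people as well as places. A paper on peer support for Pakistani mothers in an English city is UK evidence, yet its title contains a match for `Pakistan$`.

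The review informs the topic guides for the focus groups and interviews and is mapped into the intervention specification (section 6, items 1.2, 2.1 and 3.1). Section 8.1 admits all English-speaking pregnant women at 27 to 30 weeks who are considering breastfeeding, so UK evidence on barriers for these groups is in scope. Records removed by line 14 are not seen at screening, so the MEDLINE screening log would not show the loss.

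**Working it through.** No sample size, power or error rate is involved, and the plan gives no figure to reproduce. The check is of search logic.

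**Inputs (all from Appendix 1).** Line 14 has the form 13 NOT (list), in title and subject heading. The legible list has 143 terms, of which 54 end in `$` and 143 − 54 = 89 do not. A short stretch after `Mongolia$` is not legible; no term used below lies in it.

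**Step 1: what `$` does.** Stems such as `Keny$`, `Liby$` and `Morocc$` are not words, so `$` must be open-ended truncation. Hence:
- `Pakistan$` matches Pakistani
- `Bangladesh$` matches Bangladeshi
- `India$` matches Indian
- `Nigeria$` matches Nigerian
- Chinese is not truncated; it is listed as a word

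**Step 2: whether setting matters.** The NOT has no condition. A record with a listed term is removed even if it also carries a UK term.

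**Step 3: whether a later line restores it.** Line 15 is a limit on set 14 and can only make it smaller.

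**Step 4: test on titles.** Each legible term was coded as a whole-word match, with `$` open-ended, and run against titles. The first group of titles was made up to show the rule; they are not real papers.

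| Illustrative title content | Result | Term |
|---|---|---|
| Pakistani mothers in Birmingham | removed | `Pakistan$` |
| Bangladeshi women in London | removed | `Bangladesh$` |
| Indian mothers in Leicester | removed | `India$` |
| Nigerian mothers in London | removed | `Nigeria$` |
| Chinese mothers in New York | removed | Chinese |
| South Asian mothers in Bradford | kept | none |
| Somali mothers in the UK | kept | none |

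Of the six UK-set titles, four are removed and two kept. The New York title shows that Chinese acts as a population word; the same word in a UK title would be matched in the same way. Kept here means that the title does not trigger the filter. A listed term in the subject heading still would.

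**Step 5: real titles.** Six titles from the Protocol's reference list were run. One is removed: the peer-counselling trial in northeast Brazil (reference 21), a setting that the filter means to exclude. Five are kept, including the study of White British and South-Asian mothers in Bradford (reference 26).

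Whether a UK study survives thus depends on which word its title uses for the mothers and on which stems were truncated, not on where it was done.

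**The case against.** The strongest reply is that no actual loss is shown. The removed UK titles are invented, and the one real title tested on a UK minority population is kept. That stands: the fault lies in the rule, and its yield is unknown.

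Second, MEDLINE is not the only route to UK evidence. Item 1.2 also covers websites and unpublished studies. Item 1.1 extends the survey to infant feeding coordinators across the UK and asks for evaluation reports from the previous two years. Section 16 describes the current UK range from the survey. This reduces the harm but does not repair the line, since the survey cannot replace published work on theory and barriers.

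Third, section 4.1 puts White British mothers among those at highest risk, so the lost studies might be peripheral. They are not irrelevant: the same sentence also names younger and deprived mothers, and eligibility is not limited by ethnicity.

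Some stronger readings are tempting but not supported:
- **Excluding Hong Kong, Singapore or records matching "or Venezuela or developing countr" is an error.** For a rapid review in months 1 and 2 with a UK objective, these are defensible choices of scope.
- **The loss of US studies is part of the same fault.** `India$` does match Indiana, and `Georgia$` the US state, but such studies bear only on the wider search for theory, barriers and economics, not on UK provision. Removing truncation would not rescue Georgia in any case.
- **All fourteen databases are affected.** Only the MEDLINE strategy is shown, and nothing says that the filter is repeated elsewhere.

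**Conclusion.** The point holds in a narrow form. Line 14 is an unconditional exclusion whose terms match population names, so it can drop UK-set studies that name Pakistani, Bangladeshi, Indian, Nigerian or Chinese mothers in the title or subject heading. That works against Objective 1, and the Protocol gives no reason for it.

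A reader might infer that the search systematically loses UK evidence on minority-ethnic mothers. The document does not support that: terms such as South Asian or Somali do not trigger the filter, nor does a group named only in the abstract.

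The number of records lost cannot be computed. The conclusion rests on `$` being truncation, which the stems show, and on line 14 being run as printed. Severity is minor: no feasibility outcome, estimate or participant protection is affected.

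**What to change.** Make the exclusion conditional, for example:

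`13 not ((country list).ti,sh. not (United Kingdom or UK or Great Britain or England or Wales or Scotland or Northern Ireland).ti,ab,sh.)`

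This rescues a record only if a UK term stands in its title, abstract or heading; a paper that names only a city would still be lost. The alternative without that gap is to drop line 14 and exclude by setting at screening. Apply the same exemption in any other database where the country filter is used.

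The cost is one edited line and some additional titles to screen. Running the old and new lines side by side gives the exact number of added records, and so the extra work, before the change is adopted. The review is planned for months 1 and 2, so the change belongs before the search is run. If it has already been run, only the records that the new line adds need screening.

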Appendix 2: Data items and proposed methods for data collection

	Baseline (30 -34 weeks gestation)	Follow-up at 8 – 10 weeks after birth									
Data item		Telephone interview (maternal self-report)	Health Visitor	Child Health Systems	Hospital Episode Statistics	General Practice Databases					
Not in education, employment or training (NEET status) (48, 49)	x										
In paid employment (48, 49)	х										
Type of employment (48, 49)	х										
In receipt of benefits (48, 49)	х										
Other financial support (48, 49)	х										
Infant feeding intentions (45, 50)	х										
Maternal health and well-being											
General health status (EQ-5D) (51)	х	х									
Weight/Body mass index (BMI)	x	х	х								
Psychological distress (52)	x	x									
Self-efficacy (GSE) (53)	X	x									
Adaptive functioning (54, 55)	х	х									
Prenatal attachment (46)	x										
Maternal smoking	x	х	х								
BF maintenance (exclusive and partial) at 10 days and 8 weeks		х	х	х							
Mastitis		Х	х								
Primary care or secondary care admission or attendance		х	х		х	х					
BF support from usual care		х	х								
Postnatal depression (Edinburgh PDS) (56)		х	х								
Maternal satisfaction with care and feeding method		х									
Child health											
Neonatal unit admission		х	х		х	х					
Emergency attendances and admissions (all causes)		х	х		х	х					
Infections (urinary, respiratory, recurrent diarrhoea, gastro-intestinal)		х	х			х					
Primary care consultations (all causes)		х	х			х					
Referral from primary care (social care, other, safeguarding)		х	х			х					

24 References

